ECOG PS 	X	X 	X	X	X	X	X	X	2-weekly	X	X		
Enrolment (if eligible) 	X												
DLT assessment 		X	X 										
12-lead ECG	X	X	X	X	As indicated and decided by Investigator					X			
Hematology and hemostaseology	X		X	X	X	X	X	X	2-weekly	X	X		
Core serum chemistry 			X	X		X	X		2-weekly		X		
Full serum chemistry 	X				X			X	6-weekly	X			

Assessment	Clinical Screening / Baseline Assessments	Treatment Phase 								EOT Visit 	Safety Follow-up 	Long-term Follow-up 	
		≤ Day -14 to Day -1	V1	V2	V3	V4	V5	V6	V7				Until progression
			W1	W3	W5	W7	W9	W11	W13				
			D1	D15	D29	D43	D57	D71	D85				
Full urinalysis 	X									X			
Basic urinalysis 				X			X	6-weekly					
Serum beta-hCG pregnancy test (if applicable) 	X												
Urine pregnancy test (if applicable) 		X		X		X		X	4-weekly	X			
CCI													
Premedication 		X	X	X	X								
Avelumab administration		X	X	X	X	X	X	X	2-weekly				
Concomitant medication and procedures 	Collected at each study visit through the 30-day Safety Follow-up Visit												

Assessment	Clinical Screening / Baseline Assessments	Treatment Phase 								EOT Visit 	Safety Follow-up 	Long-term Follow-up 		
		≤ Day -14 to Day -1	V1	V2	V3	V4	V5	V6	V7	Until progression	Within 7 days after decision to discontinue IMP 	30 days (± 5 days) after last IMP	Phone Call 90 days (± 5 days) after last IMP	Every 12 weeks (± 7 days) 
			W1	W3	W5	W7	W9	W11	W13					
			D1	D15	D29	D43	D57	D71	D85					
AE collection 	AEs are collected through the 30-day Safety Follow-up Visit Treatment-related nonserious AEs are collected until the 90-day Safety Follow-up Phone Call													
SAE collection 	All SAEs are documented until the 90-day Safety Follow-up Phone Call Ongoing SAEs at the 30-day Safety Follow-up Visit will be followed up													
Free T4 and TSH	X				X			X	6-weekly	X	X			
PK sampling 	See Table 1-3													
ADA sampling 	See Table 1-3													
Survival 		X	X	X	X	X	X	X	Every visit	X	X	X	X	
Further anticancer therapy 											X	X	X	

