11. The observation period for DLTs is the 21-day period after the first administration of avelumab for subjects with data used for implementing the dose-escalation algorithm for dose determination (the DLT assessment is not applicable for the 6 subjects in 10 mg/kg once weekly cohort).
12. Core serum chemistry includes liver function panel (alkaline phosphatase, aspartate aminotransferase, alanine aminotransferase, bilirubin), acute chemistry panel (sodium, potassium, chloride, blood urea nitrogen/total urea, creatinine, glucose), and mineral panel (magnesium, phosphorus, calcium). If full and core chemistry are scheduled at the same visit, the full chemistry will be performed.
13. Full chemistry panel and other laboratory studies are detailed in [Section 7.4.3](#). Follicle-stimulating hormone at Clinical Screening, if applicable.
14. Full urinalysis (protein content required, and optional parameters albumin and immunoglobulin G to be tested depending on study site capability) at Clinical Screening/baseline, and EOT; basic urinalysis (protein content only) on Days 43 and 85, and then every 6 weeks thereafter prior to administration of avelumab. If urinalysis (full or basic) is positive for protein, sediment will be evaluated.
15. In serum at Clinical Screening; in urine thereafter. Results of the most recent pregnancy test should be available prior to next administration of avelumab.

CCI

CCI

21. Premedication is mandatory approximately 30 to 60 minutes prior to the first 4 doses of avelumab. Premedication should be administered for subsequent avelumab doses based upon clinical judgment and presence/severity of prior infusion reactions. This regimen may be modified based on local treatment standards and guidelines as appropriate. However, the prophylactic use of systemic corticosteroids is not permitted.
22. Concomitant medications and procedures will be documented at each study visit until the 30-day Safety Follow-up Visit.
23. All AEs will be documented at each study visit until the 30-day Safety Follow-up Visit. After this visit, only treatment-related nonserious AEs have to be documented until the 90-day Safety Follow-up Phone Call.

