## 2.1 Safety Monitoring Committee

To ensure subjects' safety during the study, a Safety Monitoring Committee (SMC) will review the safety data on a regular basis. The SMC consists of permanent members from the Sponsor (eg, but not limited to, early development lead, medical lead, and Global Patient Safety representative), the Coordinating Investigator as well as of ad hoc members (eg, but not limited to, all participating Principal Investigators [as applicable]). During the study, the SMC will evaluate the safety data and will decide on dose-limiting toxicities (DLTs) relevant for the treatment and will advise on dose escalation or suspension of enrolment, with the final adjudication being a Sponsor prerogative. In 10 mg/kg once weekly cohort, the SMC will evaluate overall safety data when all 6 subjects have completed minimum 4-week treatment period, and after 12 weeks of observation has been completed for all subjects enrolled in this cohort. The SMC may modify the frequency of meetings as deemed appropriate by the SMC during the course of the study.

The membership and specific working procedures of the SMC will be described in an SMC Charter, which will be established prior to the start of subject recruitment.

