### Dose-limiting Toxicity

A DLT is defined as a  $\geq$  Grade 3 ADR according to the NCI-CTCAE v4.03, occurring during the DLT observation period of the dose escalation cohorts. An ADR is defined in this study as any AE suspected to be related to avelumab by the Investigator and/or Sponsor. A DLT must be confirmed by the SMC as being related to avelumab.

A DLT is specifically defined as any Grade  $\geq$  3 toxicity that is possibly, probably, or definitely related to avelumab, occurring during the DLT observation period, except for any of the following:

- Grade 3 infusion-related reaction resolving within 6 hours and controlled with medical management.
- Transient ( $\leq$  6 hours) Grade 3 flu-like symptoms or fever, which is controlled with medical management.
- Transient ( $\leq$  24 hours) Grade 3 fatigue, local reactions, headache, nausea, emesis that resolves to  $\leq$  Grade 1.
- Grade 3 skin toxicity, or Grade 3 LFT (ALT, AST, or gamma-glutamyl transferase) increase that resolves to  $\leq$  Grade 1 in less than 7 days after medical management (eg, immunosuppressant treatment) has been initiated.
- Grade 3 diarrhea unless to be discontinued according to Treatment Guidelines. In this case it would be an DLT again.
- Single laboratory values out of normal range that are unlikely to be related to avelumab according to the Investigator, do not have any clinical correlate, and resolve to  $\leq$  Grade 1 within 7 days with adequate medical management.
- Tumor flare phenomenon defined as local pain, irritation, or rash localized at sites of known or suspected tumor.

The ADRs (including DLTs) that require permanent discontinuation of avelumab are described in Section 5.1.3.1.

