**Table 7-1 Required Laboratory Panel Tests**

Full Chemistry	Hematology
Albumin	Absolute lymphocyte count
Alkaline phosphatase 	Absolute neutrophil count
Alanine aminotransferase 	Hematocrit
Amylase	Hemoglobin
Aspartate aminotransferase 	Platelet count
Gamma-glutamyl transferase	Red blood cells
Blood urea nitrogen/total urea 	White blood cells and differential count
Calcium 	Red blood cell morphology (optional  )
Chloride 	Reticulocytes
Cholesterol	Mean corpuscular hemoglobin
Creatine kinase	Mean corpuscular volume (optional  )
Creatinine 	Mean corpuscular hemoglobin concentration
C-reactive protein	Hemostaseology
Glucose 	Activated partial thromboplastin time (aPTT)
Lactate dehydrogenase	Prothrombin time/International Normalized Ratio (INR)
Lipase	Hormone
Phosphorus/phosphates 	Follicle-stimulating hormone (if applicable)
Magnesium 	Thyroid-stimulating hormone (TSH)
Potassium 	Free thyroxine (T4)
Sodium 	Antibodies
Total bilirubin 	Totality of binding antidrug antibody (ADA) (Section 7.7)
Total protein	Urinalysis
Uric acid	Full: protein content  , albumin (optional  ) and immunoglobulin G (optional  )
Triglycerides	Basic (dipstick): protein content only 
Hemoglobin A1c	

Core serum chemistries.

If urinalysis is positive for protein, sediment will also be evaluated.

Urinalysis is not required for subjects with urothelial cancers.

To be assessed depending on study site capability. For urinalysis parameters, study sites not able to assess urine albumin and immunoglobulin will only test for urine protein content.

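### The DLT definition names GGT, yet no post-dose GGT, lipase, amylase or creatine kinase is scheduled inside the 21-day DLT window

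*Protocol*

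**What the plan says.** **DLT definition.** Protocol Section 7.4.1.1 states: "A DLT is specifically defined as any Grade $\geq$ 3 toxicity that is possibly, probably, or definitely related to avelumab". The event must fall in the observation period, the SMC must confirm that it is related, and seven exceptions apply. One exception covers Grade 3 skin toxicity and a "Grade 3 LFT (ALT, AST, or gamma-glutamyl transferase) increase that resolves to" Grade 1 or less in under 7 days from the start of medical management. Table 1-1, footnote 11, sets the period: "The observation period for DLTs is the 21-day period after the first administration of avelumab".

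**Panels.** Table 1-1, footnote 12, begins: "Core serum chemistry includes liver function panel (alkaline phosphatase, aspartate aminotransferase, alanine aminotransferase, bilirubin". It then lists electrolytes, urea, creatinine, glucose, magnesium, phosphorus and calcium. GGT, lipase, amylase and creatine kinase are absent. Table 7-1 lists all four under full chemistry without the core mark.

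**Schedule.** In Table 1-1 the row "Full serum chemistry" is marked at screening, V4 (Day 43) and V7 (Day 85), then 6-weekly and at the end-of-treatment (EOT) visit. V2 (Day 15) and V3 (Day 29) have core chemistry.

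**Grading.** SAP Section 18.3 gives Grade 3 and Grade 4 limits for all four analytes.

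**Review.** Under Section 5.1.2.1.2 (text with Figure 5-3), the SMC decides on escalation once all subjects of a cohort have completed the DLT period. For the weekly cohort, Section 2.1 adds that the "SMC will evaluate overall safety data when all 6 subjects have completed minimum 4-week treatment period".

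**The concern.** DLT occurrence is a primary endpoint, and escalation turns on very small counts. The definition treats an unresolved, related Grade 3 GGT rise as something that can be dose limiting, but the schedule does not draw GGT while the definition applies. The 7-day resolution test for GGT has no scheduled data behind it either. Lipase, amylase and creatine kinase share the gap. The DLT text does not name them, but the general Grade 3 rule covers them and the SAP grades them.

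The question is which analytes are run at a visit that already takes blood, not when the visits fall.

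**Working it through.** **Step 1: chemistry draws against the window (Table 1-1; window ends on Day 21).**

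| Visit | Day | Panel | Post-dose and in window? |
|---|---|---|---|
| Screening | -14 to -1 | full | no (pre-dose) |
| V1 | 1 | none | no |
| V2 | 15 | core | yes |
| V3 | 29 | core | no |
| V4 | 43 | full | no |
| V7 | 85 | full | no |

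The visit window is -3/+1 days. The Day 29 draw can move no earlier than 29 - 3 = Day 26. The first full panel on treatment can move no earlier than 43 - 3 = Day 40. That is 40 - 21 = 19 days after the DLT window closes, or 43 - 21 = 22 days nominally. Scheduled in-window post-dose values for each of the four analytes: 0.

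**Step 2: subjects affected.** The cohort sizes reproduce the planned total: 3 + 6 + 6 + 6 = 21, or 6 + 6 + 6 + 6 = 24 if the 3 mg/kg cohort is expanded. The weekly cohort is not assessed for DLTs. At 20 mg/kg the last 3 subjects are not assessed if the first 3 have no DLT. The number assessed is therefore 3 + 6 + 3 = 12 to 6 + 6 + 6 = 18, if all three levels are completed and nobody is replaced. All of them have zero scheduled in-window values.

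**Step 3: sensitivity of the rule.** One uncounted DLT can turn 1/3 (expand) into 0/3 (proceed), or 2/6 (hold) into 1/6 (proceed).

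**Step 4: illustration with assumed rates.** The documents give no event rate. Let v be the rate of DLTs that are seen and q an independent rate of events that would have counted but are not drawn. The true rate is t = 1 - (1 - v)(1 - q). The chance of passing a level is (1 - p)³ + 3p(1 - p)⁵ under the staggered rule (3 and 20 mg/kg) and (1 - p)⁶ + 6p(1 - p)⁵ in the six-slot 10 mg/kg cohort. With v = 10%:

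| q | t | Staggered: pass at v, at t | Excess | Six-slot: pass at v, at t | Excess |
|---|---|---|---|---|---|
| 2% | 11.8% | 0.906, 0.875 | 0.031 | 0.886, 0.849 | 0.037 |
| 5% | 14.5% | 0.906, 0.824 | 0.082 | 0.886, 0.788 | 0.098 |
| 10% | 19.0% | 0.906, 0.730 | 0.176 | 0.886, 0.680 | 0.206 |

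These figures show direction only. They assume that every missed event would have been judged an AE, found related, confirmed by the SMC and not exempted.

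**Step 5: weekly cohort, outside the DLT endpoint.** Table 1-2 has core chemistry on Days 8 to 36 and full chemistry first on Day 43. Four weeks end at about Day 28, and 43 - 28 = 15 days. Because the SMC waits for all 6 subjects, anyone who started about two weeks or more before the last subject may already have a Day 43 value. Later starters will not.

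**The case against.** The strongest reply is that a laboratory-only rise is not a DLT by default. A DLT is an adverse drug reaction, hence an AE. Section 7.4.1.1 says abnormal laboratory findings are not reported as AEs unless they come with signs or symptoms, lead to discontinuation, or are otherwise judged medically important. Section 5.1.3.1 also exempts Grade 3 and 4 laboratory values without a clinical correlate from withholding or stopping. This stands, and it narrows the point: for a rise without symptoms, the main route to a DLT is the investigator's judgement of medical importance. It does not remove the point, because that judgement needs a value. The exception for single laboratory values applies only when, among other conditions, they are unlikely to be related. A related one is therefore not exempt under it.

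A reader might infer that the endpoint cannot detect these toxicities at all. The documents do not support that. Full chemistry is done at the EOT visit for anyone who stops early, unscheduled tests are possible, and symptomatic events are reported as AEs. The limits are that the only analyte-specific trigger for extra draws in Section 7.4.3 is AST, ALT or bilirubin, and that its weekly-repeat rule starts only once an abnormal value has been found.

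A reader might also infer that every SMC review lacks these values. That is too broad. The weekly cohort's 12-week review follows Day 43. Its first review lacks them for certain only in later starters. In an escalation cohort, a subject who started about three weeks before the last may have a Day 43 value by the time of the review, though that value lies outside the DLT window.

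Eight SAP-graded analytes lack the core mark (albumin, amylase, GGT, cholesterol, creatine kinase, lipase, triglycerides, uric acid). The documents give no reason to treat albumin, cholesterol, triglycerides or uric acid as relevant to dose-limiting toxicity here. GGT has the firmest support, because the DLT text names it. Creatine kinase has some, since Section 3.2.1 lists myositis among the important risks. Lipase and amylase rest on the general rule and the SAP grading.

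**Conclusion.** The point holds as a mismatch between the DLT definition and the laboratory schedule. For 12 to 18 DLT-assessed subjects, the plan has no scheduled post-dose GGT, lipase, amylase or creatine kinase in the 21-day window, and the first falls 19 to 22 days after it closes. A related rise of Grade 3 or higher without symptoms can go unrecorded unless an EOT visit or an unscheduled test finds it.

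It would be wrong to conclude that any Grade 3 rise in these analytes is a DLT. Relatedness, SMC confirmation, the AE reporting rule and the exceptions all apply, and GGT itself appears only inside an exception. Nor do the documents show that an escalation decision would change. They give no event rate, and the pass probabilities above rest on assumed ones. This is a gap worth closing because closing it is cheap, not evidence that the DLT count will be wrong.

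**What to change.** Reconcile Section 7.4.1.1 with Table 1-1, footnote 12 and Table 7-1 by running full serum chemistry on the blood already drawn at V2 (Day 15). At minimum add GGT there, preferably with creatine kinase, lipase and amylase. This raises the scheduled in-window values from 0 to 1 per subject.

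State the limit of this change in the protocol. Under Section 7.4.3 blood is taken before dosing, so the Day 15 sample reflects the first dose only. The remainder of the window, Days 15 to 21, still has no scheduled value after the second dose. Adding the analytes on Day 29 would help follow resolution but does nothing for detection inside the window.

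As a secondary step for the weekly cohort, add the same analytes to the existing Day 22 draw in Table 1-2 and update footnote 8, so that every subject still on treatment has a post-baseline value before the first SMC review.

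The cost is a schedule amendment, a few local assays on samples already taken, and an occasional incidental finding to adjudicate. No new visit or staff is needed. For cohorts whose windows have already passed, the clinical study report should say that these analytes were not measured on schedule during the DLT period.

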### 5.1.3.1 Adverse Drug Reactions Requiring Treatment Discontinuation or Modifications

The following adverse drug reactions (ADRs) require permanent discontinuation or treatment modification of avelumab treatment:

- Any Grade 4 ADRs: permanently discontinue avelumab except for laboratory values out of normal range that do not have any clinical correlation.
- Any Grade 3 ADRs:
  - Withhold avelumab except for laboratory values out of normal range that do not have any clinical correlate.
  - Permanently discontinue avelumab if toxicity does not resolve to Grade  $\leq 1$  or baseline within 12 weeks of last administration or if the same Grade 3 toxicity recurs (consider consult with the medical monitor before permanently discontinuing the treatment).
- Infusion should not be given if ECOG performance status is  $\geq 3$  on the day of study treatment administration. Treatment should be discontinued if ECOG performance status has not improved to  $\leq 2$  by the next scheduled treatment administration.
- Any Grade 2 ADRs should be managed as follows:
  - Infusion should not be given in case of ongoing Grade 2 ADR on the day of study treatment administration.
  - Treatment can be resumed according to original schedule\* once ADR resolved to Grade  $\leq 1$ . Up to 2 subsequent study drug doses may be omitted. If more than 2 doses are skipped, treatment may be resumed after consultation with the Medical Monitor.

\*Original schedule is defined as “the dosing schedule calculated according to first dose”.

If dosing is delayed more than 4 weeks, treatment may be resumed after consultation with the study Medical Monitor. Any delay in dosing in excess of 12 weeks is not permitted.

Infusion-related reactions and irAEs should be handled according to the guidelines provided in Sections 6.5.5.1 and 6.5.5.2, respectively.

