Investigators must also systematically assess the causal relationship of AEs to the study treatment using the following definitions. Decisive factors for the assessment of causal relationship of an AE to avelumab include, but may not be limited to, temporal relationship between the AE and avelumab, known side effects of avelumab, medical history, concomitant medication, course of the underlying disease, study procedures.

**Not related:** Not suspected to be reasonably related to the study treatment. The AE could not medically (pharmacologically/clinically) be attributed to the treatment under study in this protocol. A reasonable alternative explanation must be available.

**Related:** Suspected to be reasonably related to the study treatment. The AE could medically (pharmacologically/clinically) be attributed to the IMP under study in this protocol.

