### **Abnormal Laboratory Findings and Other Abnormal Investigational Findings**

Abnormal laboratory findings and other abnormal investigational findings (eg, on an ECG trace) should not be reported as AEs unless they are associated with clinical signs and symptoms, lead to treatment discontinuation or are considered otherwise medically important by the Investigator. If an abnormality fulfils these criteria, the identified medical condition (eg, anemia, increased ALT) must be reported as the AE rather than the abnormal value itself.

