15.1 Dose Limiting Toxicity (DLT)

The primary endpoint of the study is:

- Occurrence of DLTs during the DLT observation period. The number and proportion of subjects experiencing DLTs will be reported by dose level based on the DLT Analysis Set (excluding 10 mg/kg once weekly cohort).

Dose limiting toxicity (DLT) refers to relevant toxicity induced by the drug during the first 21 days of treatment; excluding 10 mg/kg once weekly cohort, severity of which is clinically unacceptable, limiting further dose escalation. According to toxicity evaluation criteria in NCI CTCAE V4.03, the observation period for a DLT is the 21-day period after the first administration of avelumab for subjects with data used for implementing the dose-escalation algorithm for dose determination.

DLT data will be captured from the eCRF “ADVERSE EVENTS DETAILS” form.

The Incidence rates of DLT per each dose level during DLT observation will be presented as well as by SOC and PT. DLT summary will be based on DLT set.

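### The laboratory exception to the DLT definition is almost redundant, and related asymptomatic Grade 3 or higher laboratory values may not reach the form from which DLTs are counted

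*Protocol*

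**What the plan says.** Protocol Section 7.4.1.1 (Dose-limiting Toxicity) defines a DLT in two steps. It is first a Grade 3 or higher adverse drug reaction (ADR) in the observation period. It is then, more specifically, Grade 3 or higher "toxicity that is possibly, probably, or definitely related to avelumab, occurring during the DLT observation period". An ADR is an adverse event (AE) that the Investigator, the Sponsor or both suspect of being related, and the Safety Monitoring Committee (SMC) must confirm relatedness.

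Seven exceptions follow. The sixth covers "Single laboratory values out of normal range that are unlikely to be related to avelumab according to the Investigator", if the values also "do not have any clinical correlate, and resolve to" Grade 1 or lower within 7 days.

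Four other places bear on the same values:

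- **Causality, Protocol 7.4.1.1.** There are two levels, Related and Not related. The test is whether the event is "suspected to be reasonably related to the study treatment". SAP 15.2 reads the eCRF field in the same way.
- **Abnormal laboratory findings, Protocol 7.4.1.1.** These "should not be reported as AEs unless they are associated with clinical signs and symptoms", lead to discontinuation, or are judged medically important by the Investigator.
- **Protocol 5.1.3.1.** For Grade 3 ADRs: "Withhold avelumab except for laboratory values out of normal range that do not have any clinical correlate". A parallel exemption covers permanent discontinuation for Grade 4 ADRs.
- **SAP 15.1.** "DLT data will be captured from the eCRF" form for AE details. No other source is named.

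**The concern.** There are two linked problems.

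First, the other six exceptions remove related events by type, duration or course. The laboratory exception turns on the event not being related, which largely repeats the entry condition for a DLT. As worded, it gives no relief for a brief, silent value that the Investigator attributes to avelumab. Its word unlikely, and the three graded terms in the DLT definition, also have no counterpart on the two-level scale that sites complete.

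Second, the DLT definition counts a related, asymptomatic Grade 3 or higher laboratory value, while the reporting rule tells the site not to report it as an AE unless the Investigator thinks it important. DLT occurrence is a primary endpoint, and single events decide escalation. Two sites following different paragraphs could therefore give different DLT counts for the same result.

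**Working it through.** **Design figures.** The cohort sizes 3 + 6 + 6 + 6 give the planned 21 subjects, and 6 + 6 + 6 + 6 gives 24 if the 3 mg/kg cohort expands. These are not in dispute. The synopsis says the sample size rests on no statistical assumptions.

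**Logic check.** Take a single Grade 3 or higher laboratory value in the 21-day window that is outside the separate exception for transient Grade 3 ALT, AST or GGT rises. Classify it by five yes/no facts:

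1. Investigator suspects relatedness.
2. Sponsor suspects relatedness.
3. Clinical correlate present.
4. Resolves to Grade 1 or lower within 7 days.
5. Medically important, or leads to discontinuation.

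This gives 2^5 = 32 combinations. Three rules apply:

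- ADR = (1) or (2).
- Exception met = not (1), not (3), and (4).
- On the AE form = (3) or (5).

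The DLT definition is met when the value is an ADR and the exception is not met. SMC confirmation is assumed to follow the ADR call.

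- The exception is met in 4 of 32 combinations. In 2 of these neither party suspects avelumab, so the value was not a DLT anyway. In the other 2 only the Sponsor suspects it, and there the exception does remove an ADR.
- In none of those 4 do the DLT definition and the AE-form route disagree. Both give no DLT.
- They disagree in 5 other combinations, where the definition is met but the value is not on the AE form. These are Sponsor only, unresolved (1); Investigator only, resolved or not (2); and both, resolved or not (2). All 5 have no clinical correlate and no judgement of importance.

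The combinations are not equally likely, so these counts are not rates. They show only where the rules diverge.

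**A case the schedule can produce.** Inclusion criterion 7 admits a lymphocyte count of 0.5 x 10^9/L or more. SAP Appendix 18.3 puts Grade 3 just below 0.50. Table 1-1 schedules hematology on Day 15, inside the window. A small fall that the Investigator calls related, without symptoms, is a DLT by definition but need not be reported as an AE. (Exclusion criterion 14 may bar some such subjects if a low entry count is attributed to prior therapy.)

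**Consequence.** In a six-subject cohort with one other DLT, one disputed value moves 1/6 (safe) to 2/6 (hold), under Protocol 5.1.2.1.2.

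**Illustrative probabilities.** The documents give no event rate. Assume that each subject independently has such a value with probability p of 5% to 10%, and that there are no other DLTs.

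- Six enrolled together (10 mg/kg every 2 weeks): P(hold) = 1 − (1−p)^6 − 6p(1−p)^5. At p = 0.05 this is 1 − 0.735 − 0.232 = 0.033. At p = 0.10 it is 1 − 0.531 − 0.354 = 0.114 (unrounded terms).
- Staged cohort (3 or 20 mg/kg): P(hold) = P(at least 2 of 3) + 3p(1−p)^2 × [1 − (1−p)^3]. At p = 0.05 this is 0.00725 + 0.1354 × 0.1426 = 0.027. At p = 0.10 it is 0.028 + 0.243 × 0.271 = 0.094.

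**The case against.** Three stronger readings are tempting, and the documents support none of them.

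- **That the exception can never apply.** The ADR definition accepts suspicion by the Sponsor alone, while the exception looks only to the Investigator. Where the two differ, the exception has effect.
- **That a value kept off the form is not an AE and so cannot be a DLT.** The AE definition expressly includes abnormal laboratory findings, and Section 5.1.3.1 speaks of ADRs that are laboratory values without a clinical correlate. The conflict is between the definition and the reporting rule.
- **That such values never reach the SMC.** The Investigator may report a value as medically important, Protocol 7.4.3 has results recorded on the eCRF regardless, and the SMC reviews safety data, not only AE reports. SAP 15.1 governs the DLT table, not the escalation decision.

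It is also fair to say that exposure is limited. Only core chemistry and hematology are scheduled inside the window after dosing, on Day 15. Full chemistry, which includes lipase, is scheduled at screening and next on Day 43. Transient Grade 3 liver enzyme rises have their own working exception.

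What remains is narrower. Whether a related, silent Grade 3 or higher value is counted depends on site discretion, and no rule makes anyone compare the laboratory data with the DLT count. The discontinuation route onto the form is largely closed, because Section 5.1.3.1 exempts values without a clinical correlate.

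**Conclusion.** The point holds in limited form. The sixth exception is redundant unless the Sponsor suspects relatedness and the Investigator does not. It removes no value that the Investigator calls related, and its causality terms do not match the collected scale. Independently, a related, asymptomatic Grade 3 or higher laboratory value in the DLT window meets the DLT definition but may be absent from the SAP's only stated DLT source. A reader might infer that the exception itself causes the opposite answers. It does not: they arise for values judged related, which the exception does not cover.

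One such event can change an escalation decision. The hold probabilities (3.3% to 11.4% for six together, 2.7% to 9.4% staged) rest wholly on the assumed 5% to 10% rate and on no other DLTs occurring. They ignore any SMC decision not to confirm. The conflict in wording does not depend on them. The plan should be corrected, but this does not show that any escalation decision was or would be wrong.

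**What to change.** 1. Reconcile Protocol 5.1.3.1, the causality, abnormal laboratory findings and DLT paragraphs of 7.4.1.1, and SAP 15.1. State DLT relatedness in the categories collected on the eCRF. Either give the sixth exception a condition that does not repeat the entry requirement, or say that it is meant for disagreement between Investigator and Sponsor. Which laboratory values count as DLTs is a clinical decision for the sponsor.
2. State in the protocol and the SMC Charter that every Grade 3 or higher laboratory value in the DLT observation period is flagged to the SMC for adjudication, whether or not it meets the AE reporting criteria. This leaves the general AE rule unchanged.
3. In SAP 15.1, require a cross-check of the Grade 3 or higher hematology and biochemistry listings already planned in SAP 15.3 against the DLT table, with each in-window value accounted for. Those listings carry the first administration date and the collection date, so the check is possible even after enrolment.

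The cost is wording changes and a few extra entries per cohort. No new tests are needed.
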